Secondary population: 
To determine the safety and tolerability of venglustat when administered once daily over a 104-week period.	
Changes from baseline to Week 104 in the following:
Assessment of AEs and concomitant medicationNeurological examinationOphthalmological examinationVital signsClinical laboratory evaluations including hematology, biochemistry, urinalysis, and serologyECG
Secondary population: 
To assess the PK of venglustat in plasma and CSF.	
Plasma and CSF venglustat concentrations over the study duration and plasma PK parameters (when applicable) including C_{max}, t_{max}, and AUC_{0-24} calculated using the trapezoidal method.
Secondary population: 
To assess the acceptability and palatability of the venglustat tablet	
Acceptability and palatability assessments

Tertiary/exploratory

[figure not shown]
Objectives

[figure not shown]
Endpoints

Objectives

Endpoints

Objectives**Endpoints**

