6.4 STUDY INTERVENTION COMPLIANCE

Participant compliance with study intervention will be assessed at each visit. Compliance will be assessed by reviewing participant diary and counting returned tablets. Deviation(s) from the prescribed dosage regimen should be recorded in the eCRF.

The Investigator or designee will keep an accurate record of all IMP that is received, dispensed, and returned on a per participant basis using an IMP accountability log. Measures taken to ensure and document treatment compliance and IMP accountability include:

- Accurate recording of treatment kit number as required on appropriate eCRF page for accounting purposes.
- All medication treatment kits (whether empty or unused) are returned by the participant at each visit. In case of DTP process, the intervention units can be returned by the carrier (if defined in the contract).
- The Investigator or designee tracks treatment accountability/compliance, either by diary, or by counting the number of used treatment kits and fills in the appropriate page of the participant treatment log.
- The monitor in charge of the study then checks the data entered on the IMP administration page by comparing them with the IMP that has been retrieved and the participant treatment log form.

A participant diary will be issued to the participant at the screening visit with instructions to record any safety issue. For eligible participants, the same diary will be used to record missing doses after randomization. A brief explanation should be provided if a dose is missed. The participant should bring the diary and any remaining IMP to each clinic visit.

The site staff will review the participant diary during each clinic visit and record excursions from treatment into the eCRF. The participant diary will be retrieved when the participant finishes their participation in the study.

At the completion of the study, all IMPs will be accounted for and retained or destroyed according to regulatory requirements regarding drug accountability. Investigational medicinal products will not be destroyed unless the Sponsor provides written authorization. Authorization for destruction will be given by the Sponsor once reconciliation has been completed. Whenever possible, this destruction will occur on-site, depending on local regulations and site-specific capabilities; alternatively, IMP may be returned to the Sponsor or designee for destruction. Additional details will be provided in the pharmacy manual.

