3.6.1 Extent of exposure

The extent of IMP exposure will be assessed for the two steps analysis by the duration of IMP exposure and compliance and summarized within the safety populations.

Duration of IMP exposure

Duration of IMP exposure is defined as last IMP administration date – first IMP administration date +1 day, regardless of unplanned intermittent discontinuations. If the date of the last dose of IMP is missing, the duration of IMP will be left as missing.

The duration is defined differently for the two steps of the analysis (see [Section 3.8.2](#)):

Duration of IMP exposure for the primary analysis period is defined as:

- The last IMP administration date during the primary analysis period - first IMP administration date +1.

Duration of IMP exposure for the OLE period is defined as:

- The last IMP administration date during the OLE period - first IMP administration date during the OLE period +1 day.

In addition, overall duration of exposure to venglustat is defined as:

- The last venglustat administration date (either during the primary analysis period or OLE period) - first IMP administration date (either during the primary analysis period or OLE period) +1 day.

Duration of IMP exposure will be summarized quantitatively and categorically:

- ≥ 1 day.
- ≥ 4 weeks (1 month).
- ≥ 12 weeks (3 months).
- ≥ 26 weeks (6 months).
- ≥ 52 weeks (12 months).
- ≥ 78 weeks (18 months).
- ≥ 104 weeks (24 months).
- ≥ 130 weeks (30 months).
- ≥ 156 weeks (36 months).
- ≥ 182 weeks (42 months).
- ≥ 208 weeks (48 months).

Additionally, the cumulative duration of treatment exposure (expressed in participant-years) will be provided.

Summary of extent of exposure will be provided for the safety population as well as for the population with trial impact (disruption) due to COVID-19.

Treatment compliance

A given administration will be considered noncompliant if the participant did not receive the number of days of IMP as required by the protocol. No imputation will be made for participants with missing or incomplete data.

Percentage of treatment compliance for a participant will be defined as the number of days of IMP administered divided by the total number of days that the participant was planned to take from the first administration of IMP up to the actual last administration of IMP.

Treatment compliance will be summarized quantitatively and categorically: $<80\%$, $\geq 80\%$.

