Cases of overdose are reported in the adverse event (AE) e-CRF pages as Adverse Event of Special Interest (AESI) if symptomatic or AE if asymptomatic. The reported cases of overdose will be described in the AE analysis (see [Section 3.6.2](#)).

Acceptability and palatability

For pediatric secondary population, the acceptability and palatability of venglustat tablets will be assessed for the two steps analysis by the route of venglustat administration collected in the eCRF and the treatment compliance (as defined in the above section).

Treatment compliance of participants from the pediatric secondary population will be summarized quantitatively and categorically ($<80\%$, $\geq 80\%$) according to the route of venglustat administration (Swallowed the Tablet as Whole, Chewed and Swallowed) within the secondary safety population.

[REDACTED]

[REDACTED]

[REDACTED]

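### In the readable text of SAP 3.6.1, the paediatric acceptability summary cannot register a child who takes the tablet regularly and then refuses it for good, so it can overstate acceptability

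*SAP*

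**What the plan says.** Protocol Section 3 (Table 3) lists a secondary objective for the secondary population: "To assess the acceptability and palatability of the venglustat tablet". The amendment 06 summary of changes says it was added to align with the paediatric investigation plan commitment.

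SAP 3.6.1 gives the method for the paediatric part of that population. The two attributes "will be assessed for the two steps analysis by the route of venglustat administration collected in the eCRF and the treatment compliance". Compliance follows the general definition in the same section: dosing days achieved as a fraction of dosing days intended, where the intended days run "from the first administration of IMP up to the actual last administration of IMP". On presentation, "Treatment compliance will be summarized quantitatively and categorically", with classes below 80% and 80% or above. For children this is tabulated "according to the route of venglustat administration (Swallowed the Tablet as Whole, Chewed and Swallowed) within the secondary safety population".

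On data collection, Protocol 6.4 bases compliance on the diary and returned tablets, and says of the diary: "A brief explanation should be provided if a dose is missed".

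**The concern.** A child who will not go on taking a tablet because of its taste or texture is the plainest failure of acceptability. The compliance denominator closes on the day of the last dose actually taken, so the refusal itself leaves no trace in the score. Route does not make up for this: a child who has stopped is still classed by how the tablet was taken while it was taken.

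At stake is the reading of a named paediatric objective in a very small group. The table is laid out by route, so a reader will naturally compare whole with chewed. If one route lost more children to refusal, this table would not show it.

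**Working it through.** There is no planned rate, threshold or sample size for this endpoint, so there is no stated figure to reproduce. The check applies the SAP formula directly.

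**Inputs**
- Compliance = days administered / planned days from first dose to actual last dose (SAP 3.6.1).
- Planned treatment in Period 2: 104 weeks (Protocol 4.1), which is 104 × 7 = 728 days.
- Secondary population: up to 20 in total, which may include adults (Protocol 4.1 and criterion I 01).
- Participants aged 2 to under 18 on 15 August 2022: 13 (Protocol 2.3.1.1).

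**Step 1: every dose taken, then a permanent stop**

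| Last dose on day | SAP compliance | Same doses over 728 days |
|---|---|---|
| 14 | 14/14 = 100% | 14/728 = 1.9% |
| 28 | 28/28 = 100% | 28/728 = 3.8% |
| 84 | 84/84 = 100% | 84/728 = 11.5% |

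The SAP score is 100% whenever the stop comes. The last column shows the contrast only; it measures persistence as well as compliance.

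**Step 2: doses missed before the stop**

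| Last dose on day | Missed | SAP compliance | Class |
|---|---|---|---|
| 14 | 2 | 12/14 = 85.7% | 80% or above |
| 14 | 3 | 11/14 = 78.6% | below 80% |
| 28 | 5 | 23/28 = 82.1% | 80% or above |
| 28 | 6 | 22/28 = 78.6% | below 80% |
| 84 | 16 | 68/84 = 81.0% | 80% or above |
| 84 | 17 | 67/84 = 79.8% | below 80% |

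On-and-off refusal is therefore picked up. The blind spot is the final stop.

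**Step 3: effect on the group summary**

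The number of children who take the tablet regularly and then refuse it is an assumption; the documents give none. Suppose all other children are at 80% or above and complete the period. The SAP table then shows 100% in the upper class in every row below. The share who both took the drug regularly and did not refuse it would be:

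| Stoppers | Among 13 | Among 20 (ceiling) |
|---|---|---|
| 1 | 12/13 = 92.3% | 19/20 = 95% |
| 2 | 11/13 = 84.6% | 18/20 = 90% |
| 3 | 10/13 = 76.9% | 17/20 = 85% |

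**Step 4: does the second step recover the information?** The endpoint is also summarised at the second step. Protocol 4.1 bars participants who stopped treatment early in Period 2 from the open-label extension. A compliance figure for the extension alone would therefore contain only children who stayed on the tablet through Period 2.

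**The case against.** The strongest reply is that the public text is incomplete. Three redacted blocks follow the acceptability paragraph in SAP 3.6.1, and the text of Protocol Section 8.7, which is devoted to this topic, is not available. A taste rating or a refusal item may be there. This stands. A reader might infer that the objective is left unanswered, or that palatability is not measured at all; the documents do not support either inference.

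Second, permanent stopping can be seen elsewhere. SAP 3.6.1 reports duration of exposure in bands, so a child who stops at day 14 would appear in the band of at least 1 day and be absent from the band of at least 4 weeks. SAP 3.6.2 tabulates adverse events leading to permanent discontinuation, and SAP Appendix 2 gives main reasons for discontinuation. This stands in part. The readable text does not link these outputs to acceptability or give them by route. The Appendix 2 list is framed around randomized participants, whereas the secondary population is not randomized, and refusal over taste need not be recorded as an adverse event.

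Third, a reader might infer that the plan scores a child who refuses as a success, or that it would show high acceptability however many children reject the tablet. Neither follows. No rule equates 80% compliance with acceptable, compliance is also summarised as a continuous quantity, and missed doses before the stop lower it. A claim that one route is favoured goes too far as well: the table could hide a difference in refusal, but nothing shows that one exists, and no test between routes is planned.

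Fourth, compliance while on treatment and persistence on treatment are different quantities. Replacing the denominator would mix them and would count stops for unrelated reasons as poor acceptability. This stands and shapes the fix.

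**Conclusion.** The point holds within limits. In the readable text, neither component of the paediatric acceptability summary can register permanent refusal after regular dosing, so the summary by route can overstate acceptability and cannot understate it on this account. For an individual child the gap can be as wide as 100% against 1.9%. For the group, each such child amounts to 1/13 = 7.7 percentage points if 13 children are analysed, and at least 1/20 = 5 points at the planned ceiling.

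These sizes assume that such children exist and that they missed few or no doses before stopping. The conclusion also assumes that the unavailable text does not already add stopping or refusal to this endpoint. The endpoint is descriptive, single-arm and untested, and the co-primary analyses are unaffected. This is a minor matter, worth correcting because the correction is small.

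**What to change.** Keep the compliance definition as it is. Add to the acceptability table in SAP 3.6.1, for the paediatric secondary population and by route:

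- the number (%) who permanently stopped the study drug;
- of these, the number who stopped because of refusal, taste or swallowing difficulty, taken from the recorded discontinuation reason;
- the number with doses missed for those reasons, where the reasons are in the database.

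Compliance over the planned period may be shown as a supplementary figure for the children who stopped for those reasons, labelled as reflecting persistence. If the redacted text or Protocol Section 8.7 already provides this, a cross-reference is enough.

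The cost is a few lines of SAP wording and some added table rows; no study procedure changes. The small downsides are that reasons must be grouped, preferably by rules fixed before database lock, and that diary explanations may not all reach the eCRF: Protocol 6.4 has site staff enter treatment excursions there but does not say that the reasons are entered too.

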3.6.2 Adverse events

General common rules for adverse events

All adverse events (AEs) will be coded to a lower-level term (LLT), preferred term (PT), high-level term (HLT), high-level group term (HLGT), and associated primary system organ class (SOC) using the Medical Dictionary for Regulatory Activities (MedDRA) version currently in effect at Sanofi at the time of database lock.

The AEs will be analyzed in the following 3 categories:

- Pre-treatment AEs: AEs that developed, worsened or became serious during the pre-treatment period.
- Treatment-emergent adverse events (TEAE)s: AEs that developed, worsened or became serious during the treatment-emergent period.
- Post-treatment AEs: AEs that developed, worsened or became serious during the post-treatment period.

Similarly, the deaths will be analyzed in the pre-treatment, treatment-emergent and post-treatment periods.

The primary focus of AE reporting will be on TEAEs. Pre-treatment and post-treatment AEs will be described separately.

An AE with incomplete or missing date/time of onset (occurrence, worsening, or becoming serious) will be classified as a TEAE unless there is definitive information to determine it is a pre-treatment or a post-treatment AE.

If the assessment of the relationship to IMP is missing for an AE, this AE will be assumed as related to IMP. If the severity is missing for 1 of the treatment-emergent occurrences of an AE, the severity will be imputed with the maximal severity of the other occurrences. If the severity is missing for all the occurrences, the severity will be left as missing.

The AE tables will be sorted as indicated in [Table 9](#).

Table 9 - Sorting of AE tables

AE presentation	Sorting rules
SOC, HGLT, HLT and PT	By the internationally agreed SOC order and by alphabetic order of HGLTs, HLTs and PTs.
SOC, HLT and PT	By the internationally agreed SOC order and by alphabetic order of HLTs and PTs.
SOC and PT	By the internationally agreed SOC order and decreasing frequency of PTs ^{a, b}
SMQ/CMQ and PT	By decreasing frequency of SMQs/CMQs and PTs ^a
PT	By decreasing frequency of PTs ^a

a Sorting will be based on the venglustat 15 mg dose group.

b The table of all TEAEs presented by primary SOC and PT will define the presentation order for all other tables (eg, treatment-emergent SAE) presented by SOC and PT, unless otherwise specified.

Analysis of all adverse events

The overview of TEAE with the details below will be generated:

- Any TEAE.
- Any treatment emergent serious adverse events (SAEs).
- TEAE leading to death.
- Any TEAE leading to permanent intervention discontinuation.
- Any treatment emergent AESI.

The AE summaries of [Table 10](#) will be generated with number (%) of participants experiencing at least one event.

Table 10 - Analyses of adverse events

Type of AE	MedDRA levels
All TEAE	Primary SOC, HGLT, HLT and PT
All TEAE by trial impact (disruption) due to COVID-19	Primary SOC and PT
TEAE related to IMP as per Investigator's judgment	Primary SOC and PT
TEAE by maximal intensity	Primary SOC and PT
Treatment emergent SAE	Primary SOC and PT
TEAE leading to permanent intervention discontinuation	Primary SOC and PT
TEAE leading to death (death as an outcome of the AE as reported by the Investigator in the AE page)	Primary SOC and PT
Treatment emergent COVID-19 related AE	Primary SOC and PT
Pretreatment AE	Overview ^a
Pretreatment AESI	Primary SOC and PT
Treatment-emergent AESI	Primary SOC and PT
Post-treatment AE	Overview ^a

a Will include the following AE categories: any AEs, any serious AEs, any AEs leading to death, any AEs leading to permanent intervention discontinuation.

Analysis of deaths

In addition to the analyses of deaths included in [Table 10](#) the number (%) of participants in the following categories will be provided:

- Deaths during the treatment-emergent and post-treatment periods by reason for death.
- Deaths in non-randomized participants or randomized but not exposed participants.

Analysis of adverse events of special interest (AESIs)

Adverse events of special interest (AESIs) and other AEs of interest will be selected for analyses as indicated in [Table 11](#). Number (%) of participants experiencing at least one event will be provided for each event of interest. Tables will be sorted as indicated in [Table 9](#).

Table 11 - Selections for AESIs

AESIs and other AEs of interest	Selection
Pregnancy of a female subject	e-CRF specific tick box on the AE page / specific e-CRF page
Symptomatic overdose (serious or non-serious) with IMP	e-CRF specific tick box on the AE page / specific e-CRF page
Increase in alanine transaminase (ALT)	e-CRF specific tick box on the AE page
New or worsening lenticular opacities and cataracts	e-CRF specific tick box on the AE page

3.6.3 Additional safety assessments

3.6.3.1 *Laboratory variables, vital signs and electrocardiograms (ECGs)*

The following laboratory variables, vital signs and electrocardiogram (ECG) variables will be analyzed. They will be converted into standard international units.

- Hematology:
 - Red blood cells and platelets and coagulation: hemoglobin, hematocrit, erythrocyte count, platelet count.
 - White blood cells: white blood cell count, neutrophils, lymphocytes, monocytes, basophils, eosinophils.
- Clinical chemistry:
 - Metabolism: glucose, protein.
 - Electrolytes: sodium, potassium.
 - Renal function: creatinine, blood urea nitrogen, estimated Glomerular Filtration Rate (eGFR).
 - Liver function: alanine aminotransferase, aspartate aminotransferase, alkaline phosphatase, total and direct bilirubin.
 - Pregnancy test: Serum β -human chorionic gonadotropin (all female participants).
- Urinalysis:
 - Urinalysis for quantitative analysis: pH, proteins, and glucose.

- Vital signs: heart rate, systolic and diastolic blood pressure, weight.
 - For all Blood Pressure (BP) and Heart Rate (HR) measurements, will be analyzed using the supine measurements at each visit.
- ECG variables: heart rate, PR, QRS, QT, and corrected QTc (according to Bazett/Fridericia).

For ECG at baseline visit (V2) a triplicate of data is collected. For calculation of baseline value, the average of all available data will be calculated.

eGFR will be derived using the Chronic Kidney Disease Epidemiology Collaboration (CKD-EPI) creatinine equation for adult participants and the Schwartz formula for pediatric participants.

Quantitative analyses

For all laboratory variables, vital signs and ECG variables above, descriptive statistics for results and changes from baseline will be provided for each visit, the last value and the worst value (minimum and/or maximum value depending on the parameter) during the on-treatment period.

All laboratory parameters and vital signs parameters will be summarized using the analysis windows as defined in [Section 5.4, Table 13](#) and into account planned visit in the protocol.

When appropriate, plots of mean \pm SE over time will be presented. Plots of mean change from baseline \pm SE will also be presented.

Analyses according to PCSA

Potentially clinically significant abnormality (PCSA) analyses will be performed based on the PCSA list currently in effect at Sanofi at the time of the database lock. For parameters for which no PCSA criteria are defined, similar analyses will be done using the normal range, if applicable.

For parameters defined as efficacy endpoints, PCSA summaries will not be provided.

Analyses according to PCSA except for ECG data, will be performed based on the worst value during the treatment-emergent period, using all measurements (either local or central, either scheduled, nonscheduled or repeated).

For ECG parameter the analyses according to PCSA will used central data only.

For laboratory variables, vital signs and ECG variables above, the incidence of participants with at least one PCSA during the treatment-emergent period will be summarized regardless of the baseline level and according to the following baseline status categories:

- Normal/missing.
- Abnormal according to PCSA criterion or criteria.

For ECG, the incidence of participants with at least one abnormal ECG during the treatment-emergent period will be summarized regardless of the baseline level and according to the following baseline status categories:

- Normal/missing.
- Abnormal.

Additional analyses for drug-induced liver injury

The following additional analyses will be performed for drug-induced liver injury:

- A graph of the distribution of peak values of ALT versus peak values of total bilirubin during the treatment-emergent period will be provided.
- For each liver function test (eg, ALT), participants having experienced a PCSA (eg, ALT >5 ULN) will be summarized using the following categories: Returned to baseline PCSA status (or returned to value \leq ULN in case of missing baseline) before last IMP dose, returned to baseline PCSA status after last IMP dose, Never returned to baseline PCSA status, No assessment after elevation. This summary will be performed by categories of elevation (ALT >3, >5, >10, >20 ULN).

The incidence of liver related AEs will be summarized by study intervention group. The selection of PT will be based on SMQ Hepatic disorder.

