2.3.1.3 Syncope

In the completed placebo-controlled phase 2 study ACT14820 for GBA-PD indication, the events of syncope were more frequently observed in venglustat arm compared to placebo arm. An analysis of this information concluded that syncope is a potential risk specific for GBA-PD participants. Data were not sufficient to draw any conclusions in the other populations receiving venglustat (ie, FD, GD3, GM2).

2.3.1.4 [REDACTED]

[REDACTED]

2.3.1.5 *Transient increase in blood pressure*

In the completed or unblinded phase 2/3 studies in ADPKD, and GBA-PD indications, a transient increase in systolic (SBP) and diastolic blood pressure (DBP) was observed in the venglustat arm compared to the placebo arm. This difference peaked at Month 1 by approximately 5 mm Hg from the mean value of placebo-treated participants, and no notable difference compared to placebo was observed after 6 months. In the Phase 2 FD (Study ACT13739/LTS14116) and GD3 (PDY13949/LEAP), the SBP and DBP returned to baseline by Month 6. It should be noted that although the renal and cardiovascular systems are affected during the course of Fabry disease, based on the 3 year follow up data from the completed ACT13739/LTS14116 study, there is no evidence of disease progression and consequently no impact of the transient increase in BP on the course of disease.

In non-clinical studies, the cardiovascular system was not considered to be a target based on macroscopic and microscopic evaluation of the heart, electrocardiographic evaluations, and measurement of BP in repeat-dose studies up to 39 weeks in duration in dogs or in an in vivo cardiovascular safety pharmacology study in dogs.

Based on the above information, it was concluded that transient increase of blood pressure is a potential risk in all indications.

Blood pressure monitoring is part of the safety monitoring plan in all venglustat trials and is detailed in the SoA for this study. The management of hypertension should be in accordance with the protocol and at the discretion of the Investigator.

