8.2.3 Vital signs

- Body temperature, heart rate, respiratory rate, and blood pressure will be assessed.

- Blood pressure and pulse measurements will be assessed with a completely automated device. Manual techniques will be used only if an automated device is not available.
- Blood pressure and pulse measurements should be preceded by at least 5 minutes of rest for the participant in a quiet setting without distractions (eg, television, cell phones).
- Vital signs (to be taken before blood collection for laboratory tests) will consist of 1 pulse and 3 blood pressure measurements (3 consecutive blood pressure readings will be recorded at intervals of at least 1 minute). The average of the 3 blood pressure readings will be recorded on the eCRF.
- Ideally, pulse and blood pressure should be obtained and recorded while the participant is in the supine position as well as in the standing position. If the participant is unable to stand, blood pressure may be taken while the participant is sitting with feet dangling. If the participant is unable to stand or sit, pulse and blood pressure may be taken in supine position only.

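### Standing blood pressure and pulse are requested by the protocol, but the SAP analyses supine readings only, so measured postural changes are not summarised

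*SAP*

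**What the plan says.** **Collection.** Protocol 8.2.3 states: "Ideally, pulse and blood pressure should be obtained and recorded while the participant is in the supine position as well as in the standing position". There is a fallback when standing is not possible, namely that "blood pressure may be taken while the participant is sitting with feet dangling"; where neither standing nor sitting is possible, supine alone is accepted. The Schedule of Activities places vital signs at screening, Day 1 and Weeks 12, 26, 52, 78 and 104 of the double-blind period.

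**Analysis.** SAP 3.6.3.1 lists "Vital signs: heart rate, systolic and diastolic blood pressure, weight" and adds a rule on position, under which pressure and heart rate values "will be analyzed using the supine measurements at each visit". The by-visit, last-value and worst-value summaries apply to the variables on that list. The abnormality (PCSA) summary is scoped in the same way: "For laboratory variables, vital signs and ECG variables above, the incidence of participants with at least one PCSA". The PCSA criteria are a sponsor list in force at database lock and are not reproduced in the documents.

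**Risk background.** Protocol 2.3.1.3 reports that in the GBA-PD phase 2 study "the events of syncope were more frequently observed in venglustat arm compared to placebo arm". It goes on to class syncope as a potential risk specific to GBA-PD and says the data did not allow a conclusion in the other populations, GM2 among them. Protocol Table 2 gives neurological examination and adverse event monitoring as the mitigation for syncope.

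**The concern.** The protocol asks sites for readings in two positions, and the SAP states a rule that uses one of them. This is an explicit instruction that leaves requested safety data out of every described summary, rather than a detail left open.

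A supine reading cannot show what happens to pressure or pulse on standing; only the pair can. The question has some relevance because syncope was more frequent on venglustat than on placebo in another indication and remains unresolved for GM2. After Week 104 everyone receives venglustat, so the first 104 weeks are the study's only placebo-controlled period. If postural readings are not tabulated by arm then, the open-label extension cannot supply the comparison.

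What is at stake is completeness of the safety description. No efficacy result, sample size, power or type I error is affected.

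**Working it through.** The point rests first on a comparison of text, then on a rough estimate of how precise the added summary would be.

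**Step 1. Follow the standing reading through the SAP.**

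| Place | Content | Standing reading used? |
|---|---|---|
| Protocol 8.2.3 | Supine and standing ideally; sitting or supine-only fallback | Requested |
| SAP 3.6.3.1, variable list | Heart rate, systolic and diastolic pressure, weight | No position-specific variable |
| SAP 3.6.3.1, position rule | Supine readings for all blood pressure and heart rate | No |
| SAP 3.6.3.1, by-visit, last and worst value | Same variables | No |
| SAP 3.6.3.1, PCSA | Same variables; criteria in an external list | Not on the face of the text |
| SAP 3.6.3.2, neurological examination | Listed components include no postural pressure item | No |
| SAP 3.6.2, adverse events | Reported events by MedDRA term | No |

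The PCSA paragraph also says that all measurements are used, but it spells this out as local or central and as scheduled, nonscheduled or repeated. Posture is not mentioned. If the sponsor's list does hold postural criteria, the supine rule conflicts with them and the text still needs reconciling.

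**Step 2. Check what the stated mitigation covers.** In the double-blind period the neurological examination is scheduled only at screening and at Week 104 or early withdrawal. Adverse event tables would count reported syncope, dizziness or hypotension, but syncope is not among the events of interest in SAP Table 11. A measured fall without symptoms would not necessarily become an adverse event.

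**Step 3. Precision of an added summary.** The plan gives no figure to reproduce. The quantity is the 90% confidence interval half-width for the difference between arms in mean supine-to-standing systolic change at one visit:

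half-width = t(0.95, n1 + n2 − 2) × SD × √(1/n1 + 1/n2)

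Inputs:
- n1 = 38 and n2 = 19 (SAP section 4).
- SD of the postural change: assumed at 8, 10 and 15 mmHg, since the documents give none.
- Share unable to stand: assumed at 21%, borrowed from the wheelchair-bound share of the natural history cohort in protocol 3.1. Then 0.21 × 38 ≈ 8 and 0.21 × 19 ≈ 4, leaving 30 versus 15 with pairs.

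Multipliers of the SD:
- All 57 paired: t(0.95, 55) = 1.673; √(1/38 + 1/19) = 0.281; product 0.470.
- 30 versus 15 paired: t(0.95, 43) = 1.681; √(1/30 + 1/15) = 0.316; product 0.532.

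| Assumed SD (mmHg) | 38 vs 19 paired | 30 vs 15 paired |
|---|---|---|
| 8 | 3.8 | 4.3 |
| 10 | 4.7 | 5.3 |
| 15 | 7.1 | 8.0 |

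These figures describe precision. They are not a power statement, and SAP 3.6 plans no testing for safety.

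**The case against.** The best case for the plan is that supine is the one position expected of everyone, including participants who can neither stand nor sit, so it is a sound common basis for analysis. Standing readings are only a preference in protocol 8.2.3. That section describes one pulse and three pressure readings, with the mean pressure entered in the eCRF, and gives no delay between standing and measuring, so this is not a standardised orthostatic test. The protocol's own mitigation for syncope is neurological examination and adverse event monitoring, and the SAP analyses both. The intervals above are too wide to resolve small differences.

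Most of this stands, and it limits the point in four ways.

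- A reader might infer that postural effects are never examined. That goes too far: symptomatic events are tabulated, and only the measured change is left out.
- A reader might infer that this drug has an orthostatic syncope signal that the trial ignores. The documents do not say so. They tie the syncope risk to GBA-PD and give no mechanism.
- It is tempting to set the precision against the rise of about 5 mmHg in protocol 2.3.1.5 as if that were a supine figure. The protocol gives no position for it, and a transient rise says nothing about falls on standing, so the comparison is not made here.
- The eCRF is not visible. That standing values are stored with their position is implied by the request to record them, but is not confirmed.

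None of this explains why readings are requested in a second position and then enter no summary. Making supine the main position does not require leaving the other out.

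**Conclusion.** The point holds in limited form. SAP 3.6.3.1 analyses blood pressure and heart rate from supine readings only, while protocol 8.2.3 asks for standing readings as well where feasible. Measured postural changes are therefore not summarised, and a fall without symptoms would not be seen in the planned output.

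The change is worth making because it is cheap and because the double-blind period is the only placebo comparison for a question that the protocol leaves open in GM2. It would be a descriptive addition. Under the assumed SDs, an arm difference at a visit would carry a 90% half-width of roughly 4 to 8 mmHg: enough to show a large shift, not to exclude a small one. That range also rests on taking wheelchair use in the natural history cohort as a stand-in for inability to stand in this trial.

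**What to change.** In SAP 3.6.3.1:

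1. Keep supine as the main position.
2. Add descriptive summaries, by arm and visit, of standing systolic and diastolic pressure and heart rate, and of the within-visit supine-to-standing change, each with the number of paired readings.
3. Show sitting readings separately and flagged; do not pool them with standing readings.
4. Count participants with a postural fall, using a threshold that the sponsor specifies before unblinding.
5. State whether the vital-sign criteria in the PCSA list apply to non-supine readings.

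If the sponsor prefers not to add these, the SAP should say why readings are requested in a second position and not analysed.

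The cost is one more set of tables. No new data are needed, provided that the eCRF stores position with each reading, which should be confirmed first. Paired data will be incomplete because standing readings are taken only where possible, so the paired counts must accompany every summary.
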